Peripheral Sensory stimulation will consist of vibratory stimulation (5 minutes), and functional neuromusclular electrical stimulation (5 minutes) of the affected arm and will be administered simultaneously after the rTMS treatments.

Aim1 (testing Hypothesis 1a and 1b) Test effect of rTMS of the contralesional S1 region on sensory function The primary outcome measures will be two point discrimination. It will be collected at 3 time points during the treatment session (once before and 2 times after the rTMS: immediately after and 1 hour after. **Two-point discrimination** will be measured with Disk-Criminator disks (Baltimore, MD) by determining subjects' ability to distinguish if the touch consisted of one or two points.

Aim 2 to test Hypothesis 2: Characterize neurophysiological changes in response to rTMS of contralesional S1.. The primary outcome measure to test Hypothesis 2 we will be SEP . It will be collected at 3 time points during the treatment session (once before and 2 times after the rTMS: immediately after and 1 hour after. Somatosensory evoked potentials (SEP). SEP will be induced by stimulation of the median nerves at the wrist with a square pulse of 0.2ms delivered at 3Hz at an intensity of 2.5 times above sensory threshold but below pain threshold (Delberghe 1990). SEPs will be recorded with Ag-AgCl scalp electrodes placed on the scalp over S1 cortical region keeping impedance at $5k\Omega$ (2 cm posterior to the C3 and C4 coordinate, International 10-20 system (Nuwer 1994)), referenced to a frontocentral Fz electrode and grounded with a clavicular electrode. Location of the scalp electrodes will be digitized with Brainsight system (Rogue, Montreal) for later coregistration with the TMS data. SEP will be acquired with a Neuroscan system (Compumedics, Charlotte, NC) at a sampling rate of 1kHz using a 10 DC gain and band filtered (low pass 40 Hz, high pass 0.1 Hz, notch at 60 Hz). SEP data will be collected in blocks of 500 epochs. The N20/P30 components will be identified based on their latency and polarity and their peak-to peak amplitude measured. N20 is a negative peak within a primary sensory receptive region at 20 ms following peripheral nerve stimulus (Allison 1989, Lueders 1983). We expect to find changes in the amplitude and possibly latency of N20/P25 SEP component (Premji 2010).

Inclusion criteria

- Medically stable and at least 6 months after first ever stroke

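### Stimulating the SEP at 3 Hz, an exact sub-multiple of 60 Hz mains, leaves mains rejection to the filters; a slightly offset rate would let averaging do it and make the notch unnecessary (low priority)

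*Combined protocol and SAP*

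**What the plan says.** The Aim 2 text on somatosensory evoked potentials makes the SEP the primary outcome for Hypothesis 2, recorded once before and twice after rTMS in each treatment session. The settings that matter here are:

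- Stimulus: "SEP will be induced by stimulation of the median nerves at the wrist with a square pulse of 0.2ms delivered at 3Hz". No jitter, offset rate or mains-asynchronous trigger is mentioned.
- Averaging: "SEP data will be collected in blocks of 500 epochs".
- Acquisition: "at a sampling rate of 1kHz".
- Filters: "low pass 40 Hz, high pass 0.1 Hz, notch at 60 Hz". Slopes, phase, notch width and whether filtering is online or offline are not given.
- Measure: "The N20/P30 components will be identified based on their latency and polarity and their peak-to peak amplitude measured".
- Expected effect: "We expect to find changes in the amplitude and possibly latency of N20/P25 SEP component".

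The text names both N20/P30 and N20/P25, so both are carried through below.

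**The concern.** Averaging suppresses interference only if its phase changes from one epoch to the next. When the stimulus interval holds a whole number of mains cycles, 60 Hz and all its harmonics arrive at the same phase every time and add up as the evoked response does. More epochs at that rate do not reliably help. Protection then falls to filters, and a 60 Hz notch sits inside the band of the response: by the plan's own latencies, N20 to P30 is a 10 ms half-cycle (about 50 Hz) and N20 to P25 a 5 ms half-cycle (about 100 Hz).

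At stake is avoidable error in a small peak-to-peak amplitude compared across three time points and three sessions. How much interference survives depends on mains frequency during the block, and its phase on when the block starts, so both can differ from block to block. The notch also removes some of the signal being measured.

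**Working it through.** The plan gives no noise level or rejection figure, so there is none to reproduce. Inputs from the plan: rate 3 Hz, N = 500, mains taken as the notched 60 Hz, low-pass 40 Hz, peak gaps of 10 and 5 ms. Assumed: mains offsets, Butterworth low-pass of order 1 to 8, notch Q of 5 to 30, and equal Gaussian peaks of SD 1.5–3.5 ms.

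**1. Averaging alone.** Cycles per interval: 60/3 = 20.000, against 60/3.1 = 19.355. Fraction left = |mean over k = 0…499 of exp(2πi·f·k/rate)|. At 3 Hz a block lasts 500/3 = 166.7 s, so for a mains offset δ this is very nearly |sin(π·166.7δ)|/(π·166.7δ). For δ = 0.003 Hz: sin(0.5π)/(0.5π) = 0.637.

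| Mains offset (Hz) | 60 Hz left, 3 Hz | 120 Hz left, 3 Hz | 60 Hz left, 3.1 Hz |
|---|---|---|---|
| 0 | 100% | 100% | 0.22% |
| 0.001 | 95% | 83% | 0.22% |
| 0.003 | 64% | 0% | 0.07% |
| 0.01 | 17% | 8% | 0.02% |
| 0.05 | 3% | 2% | 0.22% |

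At 3.1 Hz the 120 Hz harmonic stays at or below 0.25% and the 180 Hz harmonic below 0.8% over these offsets. Harmonics drift faster than the fundamental, so at 3 Hz they may cancel sooner, but the plan does not control whether they do.

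**2. Adding an ideal notch at 3 Hz.** Close to 60 Hz its gain is about 2Qδ/60. The worst offset tried is 0.003 Hz. At Q = 30: (2 × 30 × 0.003/60) × 0.637 = 0.19%. At Q = 10 it is 0.06%, and at Q = 5 it is 0.03%. The low-pass then removes more. For the 60 Hz fundamental, the plan as written does at least about as well as 3.1 Hz without a notch.

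**3. Harmonics.** The notch passes over 99% of 120 and 180 Hz, so only the low-pass acts on them. Its gain is 1/√(1 + (f/40)^(2·order)):

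| Order | 60 Hz | 120 Hz | 180 Hz |
|---|---|---|---|
| 1 | 55% | 32% | 22% |
| 2 | 41% | 11% | 5% |
| 4 | 19% | 1% | 0.2% |

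At low order a noticeable share of phase-locked 120 Hz can remain. At order 4 almost none does.

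**4. Signal lost to the notch.** A causal notch placed after an order 1–4 low-pass removes about 1–5% of the low-passed peak-to-peak amplitude at Q = 30 (largest single value found 5.6%) and about 5–24% at Q = 5.

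**5. For scale, the low-pass.** On the same waveforms an order 2 or 4 low-pass alone removes about 33–66% of N20/P30 and 44–79% of N20/P25.

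**The case against.** A reader might infer that most of the mains survives into the outcome, and that a residual of amplitude A shifts N20/P30 by up to 2·sin(π·60·0.010)·A = 1.9A and N20/P25 by up to 2·sin(π·60·0.005)·A = 1.6A. The documents do not support this. Those figures ignore the filters listed in the same paragraph; with the notch on, step 2 leaves almost no 60 Hz. Nor does the plan rest on the notch alone, since the low-pass also attenuates 60 Hz. A large 60 Hz offset and a notch loss are largely alternatives, not costs to be added together.

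Other points on that side also stand:

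- 3 Hz may be nominal. A stimulator rounding the interval to exactly 333 or 334 ms would cancel a steady 60 Hz over 500 epochs. The plan specifies no such interval.
- No mains amplitude is given, so the effect in microvolts is unknown.
- A fixed notch treats every time point alike, remaining mains is unrelated to treatment condition, and session order is randomised. No bias between conditions is shown.
- The plan does not say what the 500 epochs are for; reading them as noise reduction is an inference.
- Removing the notch would leave most of the N20 distortion in place, because it comes from the low-pass.

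What the objection does not remove is the exact ratio of 20, the harmonics the notch cannot reach, and a signal loss that the stated settings do not bound.

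**Conclusion.** The point holds in a limited form. At 3 Hz with no stated jitter, averaging cannot be relied on to reject mains or its harmonics, and the plan leaves that job to the notch and low-pass together. The consequences are modest: possible phase-locked 120 and 180 Hz residue if the low-pass is shallow, and the notch loss in step 4. Both sizes rest on assumed filter order, notch Q and waveform, and the loss at any one setting could lie at the low end.

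This is added noise and some signal loss in the Aim 2 measure. It does not show that the planned SEP amplitude is materially contaminated, it gives no reason to expect one rTMS condition to be favoured, and it does not touch two-point discrimination in Aim 1. The 40 Hz low-pass is the larger threat to N20 and needs its own review. If that cut-off is raised, less protection against the harmonics remains and the stimulus rate matters more. This is a cheap improvement of low priority.

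**What to change.** In the Aim 2 SEP text, replace the 3 Hz stimulus rate with one that is not a sub-multiple of 60 Hz, for example 3.1 Hz. Keep 500 epochs, the pulse width and the stated intensity. Then measure N20 amplitude and latency on the average without the 60 Hz notch. Make the two changes together, since dropping the notch at 3 Hz would expose the 60 Hz component.

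The cost is one stimulator setting and a short edit to the text. A block takes 500/3.1 = 161 s instead of 167 s. The drawback is comparability: blocks already recorded at 3 Hz should not be mixed with new ones within a subject, so anyone part-way through should finish on the existing settings, with the settings recorded for each subject.

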Title: Can rTMS Enhance Somatosensory Recovery After Stroke?

NCT 02811913

Date : 10/8/2020

Last version of IRB-approved Research plan - 2/12/2019

Abbreviated protocol

Specific Aims. There is a confluence of evidence that supports the proposed work. First, sensory recovery is a product of brain plasticity and can be achieved even in chronic stages after stroke as demonstrated by preliminary data and evidence from the literature. Second, rehabilitation therapies can be enhanced with rTMS. Both post-stroke rehabilitation and rTMS are well established methodologies in the investigators' laboratories. Third, there is limited knowledge regarding the most effective type of rTMS (facilitatory or inhibitory) that would enhance recovery of somatosensation for individuals in chronic stages after stroke. Therefore, the main objective of this study is to test the feasibility and preliminary efficacy of a novel approach to treat sensory deficits after stroke with a combination of repetitive Transcranial Magnetic Stimulation (rTMS) and peripheral arm and hand sensory therapy. We propose to address the two study Aims by testing the following hypotheses. Aim 1: Test effect of rTMS of the contralesional S1 region on sensory function Hypothesis 1a. Facilitatory rTMS of contralesional S1 produces a greater response versus sham rTMS, according to a measure of tactile discrimination. Hypothesis 1b. Facilitatory rTMS of contralesional S1 produces a greater response versus inhibitory rTMS in improving tactile discrimination. Aim 2: Characterize neurophysiological changes in response to rTMS of contralesional S1. Hypothesis 2: Repetitive TMS of the contralesional S1 region leads to functional brain changes.

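### Aim 2's SEP is low-passed at 40 Hz, below the nominal frequency of both components the plan names, so the peaks to be measured are shrunk and displaced; bias in the pre/post comparison is not shown

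*Combined protocol and SAP*

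**What the plan says.** All of this is in the Aim 2 paragraph on somatosensory evoked potentials.

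- Role: "The primary outcome measure to test Hypothesis 2 we will be SEP". It is recorded once before rTMS and twice after (immediately and at 1 hour).
- Sampling: "at a sampling rate of 1kHz using a 10 DC gain".
- Filter: the recorded signal is "band filtered (low pass 40 Hz, high pass 0.1 Hz, notch at 60 Hz".
- Averaging blocks: "SEP data will be collected in blocks of 500 epochs".
- Measurement: "The N20/P30 components will be identified based on their latency and polarity and their peak-to peak amplitude measured".
- Definition of the first peak: "N20 is a negative peak within a primary sensory receptive region at 20 ms following peripheral nerve stimulus".
- Expected effect: "We expect to find changes in the amplitude and possibly latency of N20/P25 SEP component".

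The text gives no filter type, order or phase, no latency search window, and no second recording at a wider bandwidth. It is headed "Abbreviated protocol", so those details may have been abridged, and their absence is not counted against the plan. The 40 Hz cut-off is stated, and it is the subject of this point.

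**The concern.** A peak-to-peak measure depends on the fast swing between two adjacent peaks. If the low-pass lies below the frequency of that swing, the filter removes part of what is to be measured, and it spreads or delays the peaks. Here the peaks are found by latency, with N20 fixed at 20 ms, so a displaced peak no longer matches the definition used to find it.

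SEP is the only outcome stated for Hypothesis 2, so this setting bears on the whole of Aim 2. The plan also measures one pair (N20/P30) and expects the change in another (N20/P25). That mismatch is a separate inconsistency, but it matters here because the filter treats the two pairs differently.

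**Working it through.** **Reproduction.** The plan states no derived SEP figure, so there is nothing to reproduce.

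**Inputs from the plan.** Peak times of 20 ms (stated), and 25 and 30 ms (read from the component names); low-pass 40 Hz; sampling 1 kHz, hence an upper limit of 1000/2 = 500 Hz. Sampling therefore does not force a 40 Hz cut-off.

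**Step 1: nominal frequency = 1/(2 × interval between opposite peaks).**
- N20/P30: 1/(2 × 0.010 s) = 50 Hz.
- N20/P25: 1/(2 × 0.005 s) = 100 Hz.

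**Step 2: filter gain at those frequencies.** For a one-pass Butterworth filter of order n, gain = 1/√(1 + (f/40)^(2n)).
- 50 Hz, n = 1, 2, 4: 1/√2.56 = 0.62; 1/√3.44 = 0.54; 1/√6.96 = 0.38.
- 100 Hz, n = 1, 2, 4: 1/√7.25 = 0.37; 1/√40.1 = 0.16; 1/√1527 = 0.03.

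A real SEP is a broadband transient, so these gains only indicate the direction. Step 3 uses model waveforms.

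**Step 3: model waveforms (assumptions, not in the plan).** A negative Gaussian at 20 ms plus an equal positive Gaussian at 25 or 30 ms; SD 1.5, 2, 2.5, 3 or 3.5 ms; Butterworth order 1, 2 or 4; causal or zero-phase. That is 5 × 3 × 2 = 30 settings per pair. The zero-phase filter runs forward and backward, which doubles its attenuation, so its design cut-off was raised to 40/(√2 − 1)^(1/(2n)) Hz to keep the total at -3 dB at 40 Hz. Amplitude and N20 shift are relative to the unfiltered waveform.

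| | N20/P30 | N20/P25 |
|---|---|---|
| Amplitude kept, 40 Hz | 32-69% | 19-62% |
| Settings below half | 11 of 30 | 22 of 30 |
| N20 shift, causal | +1.8 to +10.8 ms | +1.6 to +9.5 ms |
| N20 shift, zero-phase | -0.1 to -2.2 ms | -0.5 to -4.0 ms |
| Shift above 2 ms (causal + zero-phase) | 14 + 3 = 17 of 30 | 11 + 5 = 16 of 30 |
| Amplitude kept, 300 Hz | 95-100% | 95-100% |

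At 300 Hz the N20 moves 0.05 ms or less with zero-phase filtering and 0.45-1.45 ms later with causal filtering.

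**Step 4: sensitivity to the cut-off convention.** If the two-pass filter is left uncorrected (-6 dB at 40 Hz), the losses are larger: N20/P30 keeps 27-69% (below half in 17 of 30) and N20/P25 16-62% (25 of 30). Shifts above 2 ms then number 19 and 21 of 30. A causal 4th-order Bessel filter at 40 Hz on three other waveforms kept 63-70% (N20/P30) and 42% (N20/P25), with the N20 6.5 to 7.5 ms late.

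**Step 5: what a fixed filter leaves alone.** In all 60 settings of Step 3, a 20% rise in both peaks reads as 20%, and a 1 ms delay of both peaks reads as 1.00 ms with 0.0% amplitude change.

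**Step 6: one peak moving alone (Step 3 grid).**
- A 1 ms delay of the positive peak reads as a +6 to +18% amplitude change for N20/P25 (median 15%, against 7% unfiltered) and +1 to +6% for N20/P30 (median 3%, against about 0%).
- A 1 ms delay of N20 reads as 0.45-0.80 ms for N20/P25 (0.65-0.90 unfiltered) and 0.60-1.00 ms for N20/P30 (0.85-1.00 unfiltered).

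**Step 7: signal-to-noise, 40 against 300 Hz (Step 3 grid).** Noise of the peak difference = √∫S(f)|H(f)|²·4sin²(πfτ)df over 0.1-500 Hz, with τ the filtered peak spacing. With flat noise, 40 Hz is better in 28 of 30 settings (N20/P30) and 21 of 30 (N20/P25). With 1/f noise power it is worse in 26 and 29 of 30. The plan gives no noise spectrum.

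**The case against.** The strongest reply is that Hypothesis 2 compares SEPs before and after rTMS under one filter, so whatever the filter does, it does at every time point. This largely stands. Step 5 shows that proportional changes and common delays survive, and any constant offset cancels. A reader might infer from the attenuation that the Hypothesis 2 test is biased or invalid; the documents do not support that. What remains is the case where one peak moves relative to the other. The plan allows for a latency change, but does not say that one peak would move alone. For the measured pair the leakage is modest, and for N20/P25 part of it comes from peak overlap with no filter at all.

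A second reply is that 40 Hz may raise signal-to-noise. That also stands: with flat noise it would, particularly for N20/P30. The filter cannot be called harmful to precision without a noise spectrum.

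A third is that the waveforms, filters and 2 ms threshold are the reviewer's choices. Correct. The counts describe an assumed grid and are not probabilities, and most of the large shifts come from causal filters, which the plan does not say it uses. A reader might also infer that most of the measured signal is lost. For N20/P30 less than half remains in only 11 of 30 settings; the components are attenuated and smeared, not removed. What does not depend on the grid is that both nominal frequencies exceed 40 Hz. Every filter tested cut the amplitude and moved the N20.

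**Conclusion.** The point holds in a limited form. The stated 40 Hz low-pass works against the stated measurement: both named pairs lie above it, and under the assumptions in Step 3 about 32-69% of N20/P30 and 19-62% of N20/P25 remains. The N20 moves by an amount, and in a direction, that depend on filter phase and order, which the text does not give.

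The harm is a smaller, smeared signal, peak latencies that need not match the 20 ms definition, and some leakage of single-peak latency shifts into amplitude. Bias in the pre/post comparison is not shown, and the net effect on signal-to-noise is unknown. Waveforms or filters outside the grid can fall outside these ranges. Aim 1's two-point discrimination is untouched. This is worth fixing because the remedy is cheap, but it is not fatal to Aim 2.

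**What to change.** 1. Store the SEP wide-band at the stated 1 kHz.
2. Measure peaks offline with a zero-phase low-pass well above the component band, for example 300 Hz (under the 500 Hz limit). State its order and use identical settings at all time points and sessions. If the 60 Hz notch is kept, state its width; the 300 Hz figures above do not include it.
3. Report the 40 Hz version as a sensitivity analysis.
4. Reconcile the N20/P30 that is measured with the N20/P25 in which change is expected. Name one as the Aim 2 amplitude and give a latency search window for each peak.
5. If data are already collected (the document is dated 10/8/2020), re-filter any wide-band raw data. If only 40 Hz data exist, report the filter order and phase and state the limitation.

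The cost is a filter setting and a few sentences of text, with no extra visits and no change to stimulation. The downside is more high-frequency noise per epoch, which the 500-epoch averaging reduces. If the noise is close to flat, the 40 Hz version may have the better signal-to-noise, which is the reason for keeping it alongside.
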